12.5.2. Reporting to Health Authority

After an adverse event requiring 24 hour reporting to the sponsor (per Section 12.5.1, Reporting of Serious Adverse Events to Sponsor) is submitted by the site investigator and assessed by the VCC MM and DAIT/NIAID Medical Officer, as per section 12.7, there are two options for DAIT/NIAID to report the adverse event to the appropriate health authorities.

12.5.2.1. Annual Reporting

DAIT/NIAID will include in the annual study report to health authorities all adverse events classified as:

Serious, expected, suspected adverse reactions (see Section 12.2.1.1, Suspected Adverse Reaction, and Section 12.2.2, Unexpected Adverse Event).

Serious and not a suspected adverse reaction (see Section 12.2.2, Suspected Adverse Reaction).

Pregnancies (see section 12.6, Pregnancy Reporting).

Note that all adverse events (not just those requiring 24-hour reporting) will be reported in the Annual Report.

12.5.2.2. Expedited Safety Reporting

This option, with 2 possible categories, applies if the adverse event is classified as one of the following:

Category 1: Serious and unexpected suspected adverse reaction [SUSAR] (see Section 12.2.1.1, *Suspected Adverse Reaction* and Section 12.2, *Unexpected Adverse Event* and 21 CFR 312.32(c)(1)i).

The sponsor shall report to the health authority any suspected adverse reaction that is both serious and unexpected.

The sponsor shall report an adverse event as a suspected adverse reaction only if there is evidence to suggest a causal relationship between the study drug and the adverse event, such as:

1. A single occurrence of an event that is uncommon and known to be strongly associated with drug exposure (e.g., angioedema, hepatic injury, or Stevens-Johnson Syndrome)
2. One or more occurrences of an event that is not commonly associated with drug exposure, but is otherwise uncommon in the population exposed to the drug (e.g., tendon rupture)
3. An aggregate analysis of specific events observed in a clinical trial (such as known consequences of the underlying disease or condition under investigation or other events that commonly occur in the study population independent of drug therapy) that indicates those events occur more frequently in the drug treatment group than in a concurrent or historical control group.

Certain SAEs occur commonly in this study population and will not be considered as a SUSAR unless there is evidence to suggest a causal relationship to the study intervention (IC14 monoclonal antibody).

Category 2: Any findings from studies that suggest a significant human risk

The sponsor shall report to the Health Authority any findings from other epidemiological studies, analyses of adverse events within the current study or pooled analysis across clinical studies or animal or *in vitro* testing (e.g. mutagenicity, teratogenicity, carcinogenicity) that suggest a significant risk in humans exposed to the drug that would result in a safety-related change in the protocol, informed consent, investigator brochure or package insert or other aspects of the overall conduct of the study.

DAIT/NIAID shall notify the FDA and all participating investigators of expedited Safety Reports within 15 calendar days. Unexpected fatal or immediately life-threatening suspected adverse reaction(s) shall be reported as soon as possible or within 7 calendar days.

12.5.3. Reporting of Adverse Events to IRBs/IECs

All investigators shall report adverse events, including expedited reports, in a timely fashion to their respective IRBs/IECs in accordance with applicable regulations and guidelines. All Safety Reports to the FDA shall be distributed by DAIT/NIAID or designee to all participating investigators for site IRB/IEC submission.

- Pregnancy Reporting. New pregnancies should be reported if pregnancy occurs on or before final study visit at Day 60.

While pregnancy itself is not considered to be an AE or SAE, the investigator shall be informed immediately of any pregnancy in a study participant. A pregnant participant will not receive further study medication and will be withdrawn from active participation in the study, but AEs and SAEs will continue to be monitored. The investigator shall counsel the participant and discuss the risks of continuing with the pregnancy and the possible effects on the fetus. Monitoring of the pregnant participant shall continue until the conclusion of the pregnancy.

The investigator shall report to the VCC all pregnancies within 1 business day of becoming aware of the event using the Pregnancy eCRF. All pregnancies identified during the study shall be followed to conclusion and the outcome of each must be reported. The Pregnancy eCRF shall be updated and submitted to the VCC, VCC MM, and DAIT/NIAID when details about the outcome are available.

Information requested about the delivery shall include:

- Gestational age at delivery
- Birth weight, length, and head circumference
- Gender
- Appearance, pulse, grimace, activity, and respiration (APGAR) score at 1 minute, 5 minutes, and 24 hours after birth, if available
- Any abnormalities

Any pregnancy complication such as miscarriage or elective termination of a pregnancy for medical reasons must be reported as an SAE to the sponsor as described in Section 12.5.1 Reporting of Serious Adverse Events to Sponsor (DAIT/NIAID). In addition, if the pregnancy results in a congenital abnormality or birth defect, a separate SAE report must be submitted to the VCC, VCC MM, and the Sponsor (DAIT/NIAID), using the SAE reporting procedures described above.

12.6. Reporting of Other Safety Information

An investigator shall promptly notify the VCC when an “unanticipated problem involving risks to participants or others” is identified, which is not otherwise reportable as an adverse event. The VCC, VCC MM and the DAIT/NIAID Medical Officer will review. The VCC MM will report to the IRB of record if applicable.

12.7. Review of Safety Information

12.7.1. Vanderbilt Coordinating Center Medical Monitor Review

The VCC MM will be notified by the site PI of all SAEs within 24 hours of the site becoming aware of the incident. The VCC MM shall review and make initial decisions on the disposition of the SAE and pregnancy reports received by the VCC (See Sections 12.5.1, Reporting of Serious Adverse Events to Sponsor, and 12.6, Pregnancy Reporting).

The VCC MM shall receive weekly line listing from the VCC containing cumulative information on AEs, SAEs, and pregnancies recorded by the study site(s) on appropriate eCRFs.

The VCC MM shall be available to discuss AEs and SAEs with investigators, review safety data to be delivered to DSMB, weekly safety line listing, attend DSMB meetings to participate in discussions on safety and AEs, and participate in discussions related to unblinding.

The VCC MM shall inform the DAIT/NIAID Medical Officer of all SAEs and pregnancies reported within 24 hours of notification of the event.

12.7.2. DAIT/NIAID Medical Officer

The DAIT/NIAID Medical Officer shall review and make final decisions on the disposition of the SAE and pregnancy reports received by the VCC and reviewed by the VCC MM (See Sections 12.5.1, Reporting of Serious Adverse Events to Sponsor, and 12.6, Pregnancy Reporting).

The DAIT/NIAID Medical Officer shall receive weekly reports line listing from the VCC containing cumulative information on AEs, SAEs, and pregnancies recorded by the study site(s) on appropriate eCRFs.

12.7.3. DSMB Review

12.7.3.1. Planned DSMB Reviews

To ensure participant safety and data integrity, a DSMB will be formed with members described in the DSMB Charter. The DSMB will approve the DSMB charter that will guide DSMB operations.

The DSMB will review blinded study safety data on a monthly basis. The first DSMB review of blinded safety data will occur within 30 days of the first participant treatment or when 30 participants have been enrolled, whichever comes sooner.

Two unblinded DSMB reviews are planned: first, when 75 participants have completed the 28-day portion of the study and second when 150 participants have completed the 28-day portion of the study. At each time, an unblinded safety analysis report will be prepared by the study statistician at the Study Coordinating Center and submitted to the DSMB for review. The DSMB safety reports will be based on the SAP with additional specifications as outlined in the DSMB charter. The second DSMB review at 150 participants also will be used for the interim analysis, described below (Section 13.5).

12.7.3.2. *Ad hoc* DSMB Reviews

Given the potential severity of COVID-19, there are no pre-specified study stopping rules other than the interim analysis for futility (see below). Instead there will be close oversight by the sponsor (DAIT/NIAID), the VCC Medical Monitor, the protocol chair, and monthly DSMB reviews of study safety data.

The DSMB will review any data that potentially affects safety at the request of the protocol chair or DAIT/NIAID.

After review of the data, the DSMB will make recommendations regarding study conduct and/or continuation.

12.7.3.2.1. Temporary Suspension of enrollment/drug dosing or both for *ad hoc* DSMB Safety Review

At the recommendation of the DSMB Chair, the Protocol Chair or DAIT/NIAID, a temporary halt in enrollment and drug dosing may be implemented if an *ad hoc* DSMB safety review is required. If a halt in enrollments is implemented while the DSMB *ad hoc* safety review is in progress, potential new participants will continue to be screened, consented, but not enrolled. All participants who are currently enrolled in the study will complete dosing and will continue the study monitoring and sample collection procedures, unless DSMB recommendations preclude further dosing.

13. Statistical Considerations and Analytical Plan

13.1. Overview

This is a double-blind, placebo-controlled randomized study to assess the efficacy and safety of IC14 in COVID-19 participants admitted to an acute care hospital with signs and symptoms consistent with level 5 on the 8-category ordinal scale (OS). Participants will be randomized to IC14 or placebo with 1:1 ratio and followed for 60 days after randomization. The study drug will be administered daily on Days 1-4. The randomization will be stratified by groups of study sites and concomitant use of dexamethasone or equivalent corticosteroid at baseline. All participants will receive baseline antiviral therapy with remdesivir.

13.2. Endpoints

13.2.1. Primary Endpoints

The Primary Endpoint is time to clinical recovery, defined as the time from the first dose of study drug to the first day that a participant is in categories 1, 2, or 3 on the Eight-Point Ordinal Scale through Day 28 or censored at day 28. The Eight-Point Ordinal Scale is an assessment of the clinical status on each study day. The Scale is defined as follows:

- 1) Not hospitalized, no limitations on activities

- 2) Not hospitalized, limitation on activities and/or requiring home oxygen
- 3) Hospitalized, not requiring supplemental oxygen—no longer requires ongoing medical care
- 4) Hospitalized, not requiring supplemental oxygen—requiring ongoing medical care (COVID-19-related or otherwise)
- 5) Hospitalized, requiring supplemental oxygen
- 6) Hospitalized, on non-invasive ventilation or high-flow oxygen devices
- 7) Hospitalized, on invasive mechanical ventilation or extracorporeal membrane oxygenation (ECMO)
- 8) Death

13.2.2. Secondary efficacy endpoints:

1. Days alive and free of any episodes of acute respiratory failure through Day 28 defined by need for the following oxygen delivery resource:
 - a. High-flow nasal cannula (flow rates $\geq 30\text{L/min}$ with $\text{FiO}_2 \geq 0.4$)
 - b. Noninvasive positive-pressure ventilation
 - c. Endotracheal intubation and mechanical ventilation
 - d. Extracorporeal membrane oxygenation
2. Mean change in the ordinal scale from baseline to Days 14 and 28.
3. Ordinal scale value on Day 14.
4. All-cause mortality through Days 28 and 60.
5. Proportion of participants alive and free of any episode of acute respiratory failure through Day 28.
6. Days alive and free of invasive mechanical ventilation through Day 28.
7. Proportion of participants alive and free of invasive mechanical ventilation through Day 28.
8. Proportion of participants alive and discharged from the hospital through Day 28.
9. Proportion of participants who begin corticosteroid therapy for worsening COVID-19 illness after randomization.

13.2.3. Secondary safety endpoints:

1. Safety of IC14 as measured by change from baseline in liver (alanine transaminase, aspartate transaminase, total bilirubin), renal (creatinine), hematological (hemoglobin, white blood cell count with differential), and coagulation function (platelets, prothrombin time) through Day 28.
2. Cumulative incidence of all clinical and/or laboratory adverse events through Day 28.
3. Cumulative incidence of serious adverse events through Day 60.

13.2.4. Exploratory endpoints:

1. Change from baseline in pro-inflammatory cytokines and other biomarkers in blood on Days 4, 7, 14 and 21.
2. Change in Sequential Organ Failure Assessment (SOFA) score from baseline to Days 5, 7, 14, 21 and 28.
3. Worst SOFA score from baseline to Day 28.
4. Time from baseline to improvement in one category using an ordinal scale through Day 28.
5. Time from baseline to improvement in two categories using an ordinal scale through Day 28.
6. Proportion of participants with negative nasal swabs for SARS CoV2 virus on Days 7 and 14 or at discharge if prior to Day 14.

13.3. Other Safety/Tolerability Endpoints

The safety and tolerability of IC14 will be determined by examining the toxicities and adverse events that are attributable to treatment. The safety parameters will include an evaluation of the clinical signs and symptoms from the history and physical exam, vital signs, adverse events, and safety laboratory findings (chemistries, complete blood count, platelet count). New infections will be recorded as adverse events and should include the site of infection and source of culture. Each study participant should have a complete ophthalmological examination, including slit lamp examination, when the participant is clinically stable, free of COVID-19 symptoms, beyond the COVID-19 quarantine period and able to comply with the examination.

13.4. Prognostic Biomarkers

Baseline serum prognostic biomarkers to be measured include presepsin (fragment of sCD14), sCD14, D-dimer, ferritin, C-reactive protein (CRP), and lactate dehydrogenase (LDH).

13.5. Inflammatory Biomarkers

In addition, a biomarker bank of serum and/or plasma samples will be established and stored frozen. It may be used to measure additional biomarkers, for example, but not necessarily including, procalcitonin, TNF α , IL-1 β , IL-2, IL-6, IL-7, IL-8, G-CSF, sTNFR1, sRAGE, GM-CSF, C-reactive protein, interferon-gamma inducible protein 10 (CXCL10), monocyte chemoattractant protein 1, macrophage inflammatory protein 1- α , soluble CD163, fibrinogen, triglycerides, or others.

13.6. Pharmacokinetic/Pharmacodynamic Markers

Pharmacokinetic measurements will be made of serum IC14 before infusion with measures on Days 2, 3, 4, 7 and 14. Pharmacodynamic markers will consist of a mCD14 receptor occupancy assay.

13.7. Measures to Minimize Bias

Randomization will be stratified by study site and concomitant use of dexamethasone at baseline to ensure treatment balance within each clinical center and users of dexamethasone. Block randomization with random block size will be used. The randomization schedule will be generated by the unblinded study statistician. Study participants and attending physicians will be blinded to the treatment the participants receive.

13.8. Analysis Plan

13.8.1. Analysis Populations.

The Intent-to-Treat population (ITT) is defined as all study participants who were randomized. The modified-ITT population (m-ITT) is defined as all study participants who were randomized and received at least one dose of the investigational agent. The per-protocol population (PP) is defined as all study participants in the ITT population with no major protocol deviations. Before data unblinding, the protocol chairs, the DAIT/NIAID Medical Officer and the study statistician will review all protocol deviations and produce a list of participants with major protocol deviations who will be removed from the m-ITT population for the per-protocol analysis.

Participants meeting criteria for hospital discharge will not remain hospitalized to complete a full course of study drug, but will remain in the m-ITT population, providing they were randomized and received the start of the first dose of the study drug.

The modified intention-to-treat (m-ITT) analysis will be primary and the per-protocol analysis will be secondary.

13.8.2. Analysis of Primary Endpoint

The primary endpoint is time to event (recovery defined above). Study participants who die before day 28 will be assigned the worst time to recovery (28 days); if data are analyzed while some participants are still in follow-up, the Fine-Gray approach to censoring deaths will be used (that is, participants who die will be censored based on time since randomization, with a maximum of 28 days). (Fine and Gray, 1999)

13.8.2.1. Primary Analysis of Primary Endpoint

This time to event endpoint will be tested for treatment effect (IC14+SOC vs placebo+SOC) using the stratified log-rank test, as the study will be stratified by groups of study sites and dexamethasone use at baseline.

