8.3. Study Visits or Study Assessments

8.3.1. Baseline – may be done on Study Day 1 Pre-Treatment

The following procedures must be performed, or samples must be collected, prior to study drug administration and within 24 hours of determining eligibility:

- Document reason for hospital admission.
- Document whether medical care is provided under conventional, contingency, or crisis standards of care.
- Physical examination.
- Record vital signs (height, weight, blood pressure, respiratory rate, heart rate and temperature).
- Record variables for Sequential Organ Failure Assessment score (SOFA; Appendix A).
- Determine and record Eight-Point Ordinal Scale (Appendix C).
- Draw the following clinical labs if not collected as part of clinical care: Complete blood count (hematocrit/hemoglobin, platelet count, white blood cell count with differential), PT/INR/PTT, Complete metabolic

panel (serum sodium, bicarbonate, potassium, blood urea nitrogen, creatinine, AST, ALT, alkaline phosphatase, total bilirubin), ferritin, CRP, LDH, D-dimer.

- Collect blood for study labs (15 ml blood)
 - Process and freeze (-80°C) serum for anti-drug antibodies.
 - Process and freeze (-80°C) serum for IC14 PK measurement (to be collected on 40 participants)
 - Process plasma specimens for prognostic biomarkers.
 - Collect nasal swab for viral detection.

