13.8.2.2. Secondary Analysis of Primary Endpoint

The treatment effect represented as the recovery rate ratio will be estimated using Cox proportional hazard regression. The Kaplan-Meier estimates of the recovery proportions over time will be provided to graphically present the data. Covariates to be used in the secondary analysis of the primary endpoint will be specified in the Statistical Analysis Plan and will include age and co-existing diseases, such as hypertension and diabetes mellitus.

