13.11. Sample Size Calculations

It is assumed that the placebo arm will have a similar recovery experience as shown for the remdesivir arm in Panel C of Figure 2 in the ACTT-1 study (Beigel et al. 2020). The time to recovery can be modeled using the exponential or the Weibull distribution to describe this experience. The exponential distribution assumes constant hazard and the Weibull distribution assumes the hazard decreases with time. The Weibull distribution with shape parameter 0.73 and median time to recovery of 7 days appears to fit the recovery curve better than the exponential for the remdesivir group in ACTT-1. The first column in Table 7 below assumes the Placebo arm in this study will have almost identical recovery experience as the remdesivir arm in ACTT-1. The second and the third column (median time to recovery of 6 and 5 days, respectively) assume improved recovery rate in our Placebo arm (0.882 and 0.913 versus 0.851) when factoring in corticosteroid use and evolving SOC in general. The sample size required for risk ratios ranging from 1.35-1.5, is shown in Table 7. and suggests a sample size of approximately 350 participants will have 80% power to detect a risk ratio of 1.37.

Table 7 shows the sample size needed to have 80% power with type I error rate of 0.05 to detect various RR for differing values of median days to recovery in the SOC+placebo arm. The entries in the cells show the sample size needed along with expected 28-day recovery rates in the placebo vs. IC14 arms.

Table 7. Sample Size Calculations			
	Standard of Care Group: Median Days to Recovery		
Effect (RR)	7	6	5
1.35	392 ^a 0.851 / 0.924 ^b	382 0.882 / 0.944	372 0.913 / 0.963
	312 0.851 / 0.931	302 0.882 / 0.950	296 0.913 / 0.967
1.40	254 0.851 / 0.937	248 0.882 / 0.955	242 0.913 / 0.971
	212 0.851 / 0.943	208 0.882 / 0.959	202 0.913 / 0.974

a. Sample size (n) b. Recovery rate (placebo arm / IC14 arm)

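### The primary log-rank test is valid and meets its stated 80% power, but it uses no baseline covariate beyond the strata; pre-specified adjustment could add power at no extra enrolment, by an amount that the documents do not fix.

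*Combined protocol and SAP*

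**What the plan says.** All references are to the combined protocol and SAP.

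- **Primary test (13.8.2.1).** "This time to event endpoint will be tested for treatment effect (IC14+SOC vs placebo+SOC) using the stratified log-rank test". The reason given for stratifying is the randomisation: "as the study will be stratified by groups of study sites and dexamethasone use at baseline". No other baseline variable enters.
- **Secondary analysis of the same endpoint (13.8.2.2).** A Cox model estimates the recovery rate ratio. Its covariates "will include age and co-existing diseases, such as hypertension and diabetes mellitus", with the full list left to the Statistical Analysis Plan.
- **Prognostic biomarkers (13.4).** "Baseline serum prognostic biomarkers to be measured include presepsin (fragment of sCD14), sCD14, D-dimer, ferritin, C-reactive protein (CRP), and lactate dehydrogenase (LDH").
- **Baseline collection (8.3.1).** Before study drug, sites are told: "Draw the following clinical labs if not collected as part of clinical care: Complete blood count". That list runs on to ferritin, CRP, LDH and D-dimer. The same visit has the instruction "Process plasma specimens for prognostic biomarkers".
- **Sample size (13.11).** "Table 7 shows the sample size needed to have 80% power with type I error rate of 0.05 to detect various RR". The chosen case is a rate ratio of 1.4 with a placebo median of 6 days, giving 302 participants and 278 recoveries. Enrolment may go to 350. No covariate appears in this calculation.

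**The concern.** In a time-to-event comparison, leaving out baseline variables that predict the outcome costs power even when randomisation is sound. Here the candidate variables are already obtained before dosing, and the plan already intends an adjusted Cox model. That model is secondary, so it cannot rescue a primary test that narrowly misses.

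The design has little room for this. It is sized at 80% power for an assumed rate ratio of 1.4, with no inflation for dropout. If the baseline variables carry real information about recovery, the deciding test leaves it unused. Using it would need no extra participants, visits or samples.

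**Working it through.** **Inputs from the documents.** Rate ratio 1.4, placebo median 6 days, 302 participants, 278 recoveries, 28-day recovery 0.882 and 0.950, Weibull shape 0.73, type I error 0.05 (all 13.11); 1:1 allocation (13.1); censoring at Day 28 (13.2.1).

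**Step 1: reproduce the plan's figure.** Schoenfeld's formula for 1:1 allocation:

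events = 4 × (1.960 + 0.842)² / (ln 1.4)² = 4 × 7.849 / 0.1132 = 277.3, so 278.

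This matches exactly. Section 13.11 does not say whether the test is one- or two-sided; the one-sided formula gives 219, so the plan is two-sided. Participants: 278 / [(0.882 + 0.950)/2] = 278 / 0.916 = 303.5, against 302 stated. Power at 278 recoveries: Φ(½ × √278 × ln 1.4 − 1.960) = Φ(0.845) = 80.1%.

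**Step 2: approximate the gain.** Assume that the added covariates explain a share R² of the variance beyond the strata, and treat the information as 278/(1 − R²) recoveries at the same rate ratio. The documents give no R², so a range is shown.

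| Assumed R² | 278/(1 − R²) | Power | Gain over 80.1% (points) | Recoveries for about 80% |
|---|---|---|---|---|
| 0% | 278.0 | 80.1% | 0 | 278 |
| 2% | 283.7 | 80.9% | 0.8 | 273 |
| 5% | 292.6 | 82.1% | 2.0 | 265 |
| 10% | 308.9 | 84.1% | 4.0 | 251 |
| 20% | 347.5 | 88.0% | 7.9 | 223 |
| 25% | 370.7 | 90.0% | 9.9 | 209 |

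**Step 3: check by simulation.** Setting: 302 participants, Weibull shape 0.73, placebo median 6 days, censoring at Day 28, one normal baseline score, 6,000 trials per row. The conditional effect was tuned so that the unadjusted rate ratio stayed near 1.4. The unadjusted log-rank was compared with a Cox model containing the score. Gains come from unrounded rates.

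| Assumed hazard ratio per SD of the score | Unadjusted | Adjusted | Gain (points) |
|---|---|---|---|
| 1.00 | 80.3% | 79.9% | −0.4 |
| 1.22 | 81.3% | 83.2% | 1.9 |
| 1.35 | 80.5% | 84.7% | 4.2 |
| 1.49 | 79.6% | 87.0% | 7.3 |
| 1.65 | 79.9% | 89.6% | 9.6 |

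The Monte Carlo standard error of one power is √(0.8 × 0.2/6000), about 0.5 points. With no treatment effect, the rejection rate was 4.8% to 5.0% for both tests.

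**Step 4: the downside if the covariates are useless.** With five non-prognostic covariates in the model (2,500 trials), power was 79.5% adjusted and 79.6% unadjusted, and the rejection rate under the null was 5.1% against 5.0%.

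**Limits.** The simulations in Steps 3 and 4 include neither strata nor deaths, and Step 3 uses one combined score. With eight strata (assumed, since the number of site groups is not stated) and stratified tests, power rose from 77% to 82% at 1.35 per SD and from 78% to 88% at 1.65. The two strength scales are not interchangeable. On a log-hazard scale with error variance π²/6, hazard ratios of 1.22 and 1.65 per SD correspond to shares of 2.4% and 13.2%, so Step 2 is a planning approximation rather than a calibration of Step 3.

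**The case against.** **The planned test is not wrong.** A log-rank test stratified by the randomisation factors is valid, and Step 1 shows that it delivers the stated power without covariates. This stands in full. The point is an efficiency gain not taken, not a sample-size error.

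**The size is assumed.** A reader might infer that the trial gives up 2 to 10 points of power as a matter of fact. The documents do not support that: they give no R² or hazard ratio for any covariate. A score at 1.65 per SD implies that patients one SD above and one SD below the mean recover at rates differing 1.65² = 2.7-fold. That is demanding in a population described in 13.1 as level 5 at entry, with dexamethasone already in the strata. The near-zero case belongs in the range.

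**Attenuation is not bias here.** A reader might also infer that the unadjusted rate ratio is wrong, or that true power is below 80%. The 1.4 enters section 13.11 with no covariates, so it is naturally read as the unadjusted ratio, for which power is 80.1%.

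**CRP and LDH are not shown to predict recovery.** This is correct. Section 13.4 offers only the label. The predictor data in section 1 concern ferritin and IL-6, with death as the outcome. The choice among the labs is therefore a judgement, but Step 4 shows that a poor choice costs almost nothing. Presepsin and sCD14 are less practical, because section 10 has stored samples analysed in batches after the last participant completes.

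**Adjustment is already planned.** It is, in 13.8.2.2, but only as a secondary analysis, which does not decide the trial.

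**The estimand changes.** An adjusted Cox model gives a rate ratio conditional on the covariates. This stands, but a covariate-adjusted stratified log-rank test avoids it.

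**Conclusion.** The point holds as a recommended improvement. The primary test in 13.8.2.1 is valid and meets its stated 80% power, yet it ignores age and baseline labs that are obtained before dosing and that the plan itself calls prognostic.

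The gain from pre-specified adjustment is about 0 points if the covariates carry no information, 0.8 points at 2% of the variance beyond the strata, and about 2 to 10 points at 5% to 25%. In the plan's own Weibull setting, simulation gives 1.9 to 9.6 points for a score with a hazard ratio of 1.22 to 1.65 per SD, with type I error at about 5%. Everything beyond the zero case rests on an assumed prognostic strength. The case for acting is the asymmetry: almost nothing is lost if the assumption fails, and several points are gained if it is even moderately right.

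**What to change.** In 13.8.2.1, make the primary test covariate-adjusted and stratified by the randomisation factors, two-sided at 5%.

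- **Covariates, fixed before unblinding:** age as a continuous variable, log baseline CRP and log baseline LDH from the baseline clinical labs, plus hypertension and diabetes as already named in 13.8.2.2.
- **Missing baseline labs:** fill with the median pooled over both arms, so that nobody is dropped.
- **Method:** either a covariate-adjusted stratified log-rank test, which keeps the unadjusted null hypothesis, or a stratified Cox model, with a statement that its rate ratio is conditional on the covariates.
- **Sensitivity analysis:** keep the unadjusted stratified log-rank test.
- **Tables 6 and 7:** leave as they are and label them as unadjusted planning figures.

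The cost is protocol and SAP wording, simple imputation of a few labs and, if the Cox model is chosen, a conditional rather than an unadjusted rate ratio. No participants, visits or samples are added.
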